#### Sample Size Secondary outcomes

We expect that the effect size of SFH on smoking restrictions at home will be close to what we observed in our feasibility study in Leeds. Our before-and-after study found that smoking in the presence of children had more than halved in households with at least one smoker; 42% at baseline, 20% at 6 months. We also found that the proportion of households reporting being completely smoke free increased from 35% at baseline to 67% at 6 months (52). Accordingly, a sample size of 732 and 386, respectively, are needed to detect such differences at  $\alpha = 0.01$  and  $\beta = 0.9$ .

18

It is difficult to predict the effect size (and therefore estimate appropriate sample size) of SFH on children smoking initiation and adults smoking cessation rates as there are no relevant experimental studies to our knowledge. We, therefore, predict our effect size based on longitudinal studies. For adult smoking cessation our assumption is based on a recent systematic review of longitudinal studies examining the influence of smoke free homes on adult smoking. It revealed that living in smoke free homes can increase the smoking cessation rates by four-fold in 12 months(53). Using the study(54) mentioned in this review we estimate that a sample size of 1550 would be sufficient to detect statistically significant smoking cessation at 12-moths in people who smoke between 5-14 cigarettes a day and a sample of 980 would be sufficient for smokers who smoke >14 cigarettes a day.

We base our assumptions for the predicted effect size on smoking initiation rates among young people on another longitudinal study that followed up children for four years and found that children living in houses with smoking restrictions are less likely to start smoking when they have smoking parents (1.56; 95% CI 1.15, 2.13) as well as non-smoking parents (OR = 1.75; 95% CI 1.29, 2.37)(24).

High attrition rate can be detrimental in detecting any change in children's smoking initiation and adults' smoking cessation rates in the follow-up assessments. However, we expect to trace and follow up at least 72% (1440 out of 2000) of children from primary to secondary schools. We base this on the attrition rates observed in study carried out by Rudolph et al in Leeds(42). A systematic review of school-based smoking prevention trials with long-term follow-up showed a median attrition rate of 38% in eight studies with an average follow-up period of six years(55). A 10% attrition rate every year will still leave us with 50% children followed up for the entire duration of the study.

#### **Usefulness of secondary outcomes**

- SO1 Smoking restrictions at home- A child completed questionnaire based assessment of smoking restrictions at home will provide more information on the various types of restrictions imposed at home, which will help us to better define the various categories identified primarily by estimating cotinine levels (primary outcome). It will also test the validity of the use of questionnaire based assessment of smoking restrictions as a stand-alone assessment for future research and evaluation of smoke free homes programme.
- SO2 Children's attitude and behaviours towards smoking- In our review of the literature, we found no studies that assessed the effect of interventions designed to establish smoke free homes on the smoking behaviour of young people. There is also a lack of longitudinal studies investigating the relationship between a smoke free home environment and the attitude and behaviour of young people towards smoking. We wish to measure this outcome to address this knowledge gap.
- Smoking status of adults: There is some evidence (based on observational studies) to suggest that a smoke free environment is associated with quitting smoking.
  However, again we were not able to identify any longitudinal or experimental studies of the influence of smoke free homes on adult smoking behaviour.

SO4, SO5, Quality of life and school attendance: We wish to measure these secondary outcomes to account for other related benefits that smoke free homes may have on improving children's health, quality of life, and school attendance..

## **Statistical analysis**

The analysis plan will include:

- Preliminary analysis consisting of a series of descriptive tables summarising; (a) basic characteristics of the data collected; (b) baseline characteristics of schools and children; (c) attrition rates; and (d) intra-cluster correlation coefficient for the outcomes. This will also include a comparison between participants with detectable levels of cotinine at baseline and zero levels of cotinine at baseline.
- A comparison of the means of the main outcomes at both cluster and individual level after adjusting for the cluster design. We will also adjust for the baseline characteristics and other covariates using generalised estimating equations.

We will only be measuring the salivary cotinine levels of a sample of children at follow up (90% of children who test positive for cotinine at baseline and 10% of children who test negative for cotinine at baseline).

Our principal analysis will be an adjusted analysis of salivary cotinine levels (for children who test positive for cotinine at baseline and remain in the trial – 90% of children who test positive for cotinine at baseline will remain in the trial). Consequently we do not need to adjust the main outcome for multiple testing. For all secondary outcomes we will adopt a more conservative p value (i.e., p = 0.01) to reduce the risk of a type 1 error. We will adjust for the minimisation variables and In terms of the secondary analyses we will adjust for minimisation factors and baseline measures if taken (e.g., quality of life). We will estimate a difference in the mean of salivary cotinine of all children irrespective of their smoking status.

A detailed plan will be produced before any analysis has taken place. We do not anticipate a high attrition and we will use multiple imputation methods for any attrition that does occur. A sensitivity analysis will be undertaken to assess whether or not different methods produce different results (e.g. complete case analysis vs multiple imputation). At this stage it is difficult to specify all variables on which to undertake sub-group analyses or test for treatment interactions; however these are likely to include interaction terms for: baseline cotinine values; gender of child; and certain other variables. Only the primary analysis (4 weeks post intervention - cotinine testing) will use a p value of 0.05 other analyses will use p = 0.01. We acknowledge that these sub-group analyses as hypothesis generating.

Our principal analysis will be an ITT analysis – if children move school we will attempt to follow them up in their new school for the primary outcome and, if appropriate, for secondary outcomes. Per protocol analyses can be biased so we will avoid these. However, if there is significant noncompliance with the protocol by schools or pupils we will use Complier Average Causal Effect (CACE) analysis to adjust for non adherence to the protocol, which will, in principle, produce an unbiased estimator. The statistical analysis will be carried out using STATA statistical software and R language (www.r-project.org).

It is potentially possible that some of the children in our study are established smokers and will therefore generate analytical issues. We expect such children to be small in number. However, we

can carry out a further sub-analysis to assess its effect on the outcomes. Our five-point smoking uptake and behaviour assessment questionnaire can identify both experimenters and established smokers. Besides, cotinine estimates can distinctly differentiate between active and passive smokers. In the analysis, we will adjust for baseline covariates. We will use CACE analysis to deal with nonadherence to the intervention, which adjusts for another source of possible confounding. Furthermore, we will use multiple imputation methods in a sensitivity analysis to adjust for missing data.

#### Clustering in secondary schools and families

A cross-classified mixed model approach will be used for outcomes measured at the secondary school level to account for the additional clustering at the secondary school level. (This approach is used since students attending the same primary school might not necessarily attend the same high school).

As children will move to secondary schools in the follow up years, they will not remain in their original clusters. However, this will not pose any problems for the statistical analysis. We will still use cluster specific methods for analysing secondary outcomes based on the primary school clusters. Given that children will be randomised on the basis of their primary schools and the intervention will have finished before they move on, only these will be the relevant clusters for the statistical analysis. We expect that as children grow up and move into new schools their smoking behaviour will be influenced by other factors (e.g. new peer networks) independent of the original clusters. However, we expect these factors to have a non-differential influence on children both in the control and intervention arms.

#### Sensitivity Analysis to take into account qualitative work

We will carry out a sensitivity analysis to take into account that 30 families in the intervention arm will be interviewed for the qualitative part of the study. As detailed below, these 30 families will be matched with 30 comparable families in the control arm. We will carry an additional analysis that excludes children of those 60 families in the analysis.

## **Qualitative Study**

A variety of qualitative methods will be employed in order to meet Objective 3.

1. To assess the integrity and fidelity of the implementation process and other contextual factors that might contribute to the variation in outcomes

## **Methods**

The qualitative component will support the trial by:

1) conducting focus groups to explore parents', teachers', children's, and SFH coordinators' views towards the interventions and to identify themes to inform observational protocols and interviewing guides;

2) using observational methods to investigate the engagement and educational process of SFH to ensure implementation integrity and fidelity;

3) exploring contextual factors at two levels: a) the neighbourhoods of the selected sample of families by geographical mapping b) the families' dynamics, interactions, and resulting behaviours in relation to the SFH messages through family interviews.

Research activities will be planned in step with the trial in the following stages:

#### Engagement and participation

In order to understand the process by which parents and teachers are engaged in the trial, we will conduct four focus groups in which parents, teachers at participating schools, children and SFH facilitators will be invited respectively to share their views, expectations and concerns about the intervention, and what might motivate families to be involved in the trial.

**Sampling strategy**: The members of the parent focus groups will consist of existing smokers, men and women with children attending participating schools. The teachers' focus group will comprise teachers from participating and invited schools. Healthy schools coordinators, PSHE coordinators or KS2 managers will be invited to join. The children's focus group will consist of Year 5 and 6 pupils from participating schools. These focus groups will be conducted prior to the intervention. 7-8 participants will be invited to join each focus group. Focus group interviews will be audio-taped and transcribed verbatim. Results will be analysed to inform observational protocols for SFH activities and the construction of family interviewing guides. The SFH facilitators' focus group will be held after the intervention has been delivered. This is to enable SFH facilitators to share their experiences of delivering SFH.

#### Observing the process of SFH intervention

Observational protocols will be constructed with reference to information gained from the focus groups. We will observe 6 intervention sessions delivered by the SFH project workers. Sampling strategy: selection of intervention sessions will be based on year groups of pupils and school/neighbourhood contexts - Year 5 and 6 sub-divided into inner-city, suburb and small town environments. Other observations will also be made on the delivery of message reinforcement at: a) teachers training session; b) briefing sessions at school assemblies; and c) school-based family events.

Understanding the influence of contextual factors: Neighbourhood and the Family. Context is both material/structural context and familial context in this study (56). The former is typified by features of neighbourhoods that are pro-smoking or anti-smoking i.e. organisations or agents through their regular activities encourage the uptake, maintenance, or prevention of smoking e.g. tobacco sellers, local sport clubs, convenience stores. The latter is defined by the number of smokers at home and the family power dynamics with which the intervention will interact.

**Neighbourhood mapping:** A neighbourhood mapping study will be conducted in order to find out how children in participating schools perceive the environment in which they live. Three schools will be selected to take part in this study, one from each of the categories of neighbourhood (inner-city, suburban and small town). In these schools, focus groups will be conducted, with a maximum of twelve children in each focus group. The focus groups will take the form of a mapping exercise. Participants will be provided with a GIS map of the area (1 mile radius from school). They will be asked to populate the map with identified features which are of significance and relevance to them in relation to smoking e.g. features of access to smoke free public spaces and agents that act as either enforcers or interrupters of smoking.

**Family interviewing:** The family interviewing method is based on the family theory derived from family therapy(57), and previous work in this area(58). Different concepts are used in different family theories. We will investigate the extent to which concepts of the structure and composition (number of parents, siblings, age and gender), locus of control, interaction in the family, and the wider environment (neighbourhood) will influence the adoption of SFH and the change and maintenance of smoking behaviours. We will select thirty families from the intervention arm who will be interviewed before the intervention (baseline) and after the intervention (Follow Up 1). We will also carry out follow-up interviews at each follow up point. The interviews will explore the process families go through in adopting SFH. Specifically, they will explore (i) the motivating factors that convince families to adopt SFH e.g. protecting children from SHS (ii) learning outcomes from SFH materials and behavioural actions to create and maintain smoke-free homes e.g. negotiation within family (iii) the strategies that families take in implementing SFH e.g. degree of restriction in the home, change of smoking behaviour, banning visitors' smoking (iv) impact on the smoking behaviour of the child and families as a whole e.g. taking up or quitting smoking.

**Sampling strategy**: The purpose of the sampling strategy is to explore the journey of each child and their families in a variety of contexts as they participate in the trial, and the relative significance of family and neighbourhood contexts. Therefore, it is necessary to employ a flexible and maximally expansive approach to sampling.

There will be a total of 30 families in the sample. Using the baseline results, we will select six children from each of the following five categories of smoking behaviours: (i) Non-susceptible non-smokers, (ii) Susceptible non-smokers, (iii) Early experimenters, (iv) Advanced experimenters, (v) Established smokers. Included in the sample are 5 categories of children from non-smoking families (see shaded column of figure below), who are identified by surveys and salivary Cotinine testing to have the listed behavioural types. These families (the non-smoking families) will form useful comparators. Schools will be selected from three categories of neighbourhood: inner-city; suburban and small towns. For example schools from districts of Leeds such as Harehills and Chapletown would be classified as inner city, suburbs of Leeds such as Moortown and Cookridge would be suburban, while Keighley or Shipley near Bradford would be classified as small towns . Ten families of different types (including the 5 non- smoking families) will be drawn from each of inner-city, sub-urban and small town settings identified.

In order that the qualitative work undertaken with participants can be taken into account in the trial analysis, the trial coordinators will identify a minimum of 3 pairs of schools from the schools randomised. The pairs will be chosen in order to ensure that: of the intervention schools, there is

one school in an inner-city location, one in a suburban location and one in a small town location and of the control schools, there is one school in an inner-city location, one in a suburban location and one in a small town location.

The trial coordinators will then provide the qualitative researchers with a set of a minimum of three intervention schools and a set of a minimum of 3 control schools, but will not inform the qualitative researchers which set is intervention and which set is control. The qualitative researchers will select 30 families from each set of schools, following the sampling strategy detailed above. The trial coordinators will then inform the qualitative researchers which schools were intervention schools, the 30 families selected from the set of intervention schools will form the qualitative sample. The 30 families selected from the set of control schools will be used as controls when the qualitative work with participants is taken into account in the trial analysis.

Child	Household type					
smoking	2 adults	1 adult	2 adults (at	2 adults	1 adult (non-	Adult (non
intention &	(at least	(smokes)	least one	(both	smoker) +	smoker) +
behaviour	one		smokes) +	smoke) +	children	child non
	smokes)		children (at	child (non	(smoker(s))	smoker
			least one	smoker)		
			smokes)			
NSN (i)	A1	B1	C1	D1	E1	F1
SN (ii)	A2	B2	C2	D2	E2	F2
EE (iii)	A3	B3	C3	D3	E3	F3
AE (iv)	A4	B4	C4	D4	E4	F4
ES (v)	A5	B5	C5	D5	E5	F5

These criteria for selection are designed to be maximally expansive; the aim is to include as many different types of family as possible. Flexibility in the application of the criteria is essential. It is not possible to know in advance whether the baseline data will yield results identifying potential participants to fit the criteria exactly as laid out here. In the case that there are no participants available in any one of the specified categories, we will alter some of the criteria, maintaining as much difference between family types as possible. For example, it may be that the cotinine sample results do not reflect all five categories of behavioural intention included in the sampling frame. In this case, it will become necessary to collapse these categories into reasonable behavioural types that are sufficiently different to have theoretical value.

#### Data collection from focus groups, observations, and family interviews

Focus group interviews will be conducted at schools or community centres using a guide. Family interviews will be conducted at the homes of selected families (or a mutually convenient alternative location) using a semi-structured guide. The focus groups and interviews will be tape recorded and transcribed verbatim. Researchers will also record field observations on protocols. Field notes will be regularly maintained.

#### Analysis of data from focus groups, observations, and family interviews

Using a thematic approach(59), a codebook of major themes will first be developed. Two coders will code each transcript independently. Codes will be compared and discrepancies will be resolved by

consensus. Data will be fed into NVivo.8 (qualitative analysis software). These codes will then be grouped and re-grouped to generate themes.

With the family interviews, a formative analysis will help to understand the relationship between the types of smoking behaviours of the child and his/her family and the neighbourhood context at the baseline assessment stage. Outcome matrices (see indicative matrix below) will be created based on results from assessments from the trial to facilitate analyses of themes and the similarities and differences between the typography of families and neighbourhood contexts by outcomes (e.g. household smoking restriction, exposure of SHS, change of smoking status of children & families) at each stage of the trial for each case and across cases to explore plausible explanations of the variation in outcomes.

Family type	Outcomes				
Child's smoking behaviour and intent	Impose and sustain SFH partially	Imposed and sustain SFH completely	Exposure to SHS	Taking up of smoking	Adult changing smoking behaviour
A1-F1					
A2-F2					
A3-F3					
A4-F4					
A5-F5					
Context	Neighbourhoods/ availability of smoke free environment inner-city/ suburban/small town				

The analyses will foreground the processes, negotiations and shared meanings in families, rather than focusing on the individual child or on aggregate patterns of family behaviour. This is to avoid the implicit assumption that it is the child's responsibility to persuade the family to adopt SFH. We can centralise the dynamics of 'family' in our family theory relating to smoking behaviour; explaining the variety of outcomes obtained from the trial. It is important to recognise that the analyses will be recursive, cycling back and forth between cases and outcomes.

#### Interviewing skills and conduct

Like the focus group method, family interviewing data are developed in interaction(57) and we do not intend to elicit private thoughts and opinions of individual family members. We anticipate that the researcher's presence will affect family members' responses. We will take care to put the family at ease when eliciting multiple and perhaps conflicting views while remaining engaged with the entire family and avoiding appearing to align or coalesce with any particular sub-group. It will be important to ensure that the researchers are fully trained in family interviewing. While researchers will try their utmost not to provoke conflicts or to trigger distress among the interviewees, situations may arise in which families may be in need of brief intervention. In such cases, they will be referred to a family counsellor.

## **Economic Evaluation**

An economic evaluation had been designed to meet Objective 4.

2. To estimate the cost-effectiveness and understand the budgetary implications of SFH in obtaining its intended outcomes

## **Methods**

This component of the study will estimate the cost of providing the intervention in schools. These costs will include the time of staff involved in programme delivery and materials costs. The estimated costs will be combined with outcome rates to compute a cost-effectiveness ratio. This will take the form of a cost per smoke free child (defined as having zero cotinine levels). However, most of the benefit of this intervention is likely to be in the longer term, with substantial health benefits accruing to the children and possibly their parents. Consequently, we will need to undertake economic modelling to capture these longer term impacts. The longer term follow up will provide estimates of the number of pupils who do not take up smoking in the intervention groups over and above the control scenario. These data can be combined with Quality Adjusted Life Year (QALY) estimates indicating the expected quality of life for smokers and non-smokers to project the potential QALY gains in the intervention group for those pupils who do not take up smoking. We will obtain QALY estimates from the existing literature. Thus, we will assess the QALY losses due to smoking and then estimate the gains that would be achieved should we demonstrate a significant reduction in smoking uptake. The data will also allow the modelling of potential health care cost savings amongst this population, as smokers are known to impose considerable costs on the NHS due to the treatment of smoking-related disease. These costs were estimated at £5.2 billion for the UK in 2005-6, some 5.5% of the total health care budget(43). We will produce Cost Effectiveness Acceptability Curves (CEACs), where we will plot the probability of the intervention against the willingness to pay for a QALY. The current decision rule is that if the cost per QALY has a 50% or greater probability of being less than £20,000 per QALY this is deemed to be cost effective. All future costs and outcomes will be discounted at a rate of 3.5%; however, this will be varied in a sensitivity analysis. We will undertake extensive sensitivity analyses one of which will be a threshold analysis. This will help in estimating the minimum long term effectiveness required by the programme to justify costs.

Individual cost and outcome data will be bootstrapped to adjust for the expected skewness in the distributions. The bootstrapped data are then used to construct cost-effectiveness acceptability curves that estimate the probability of the intervention being the preferred option based on uncertainty in the threshold value of the outcome domain. The trial data will be modelled using existing quality of life values based on smoking status and age, which will be projected forward to construct the expected QALY gains as a result of changes in smoking behaviour. The model will incorporate an extensive sensitivity analysis which will generate cost-effectiveness estimates based on different parameter values. The sensitivity analysis will be important to the model since many of the modelled parameters will be literature based estimates which are used to extrapolate the data from the trial. The modelling will adjust for natural quit rates in the population, so those smoking who would have given up anyway will be accounted for. Qualitative data will also inform about changes in the locations of smoking and thus the impact of passive smoking as well and quitting.

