#### Justification for long follow-up

According to the General Household Survey 2007, 38% of regular adult smokers started smoking before the age of 15 years (38). The smoking prevalence among those aged 11-15 years increases up to the age of 15 according to the 2008 Smoking, Drinking and Drugs survey carried out by the National Centre for Social Research (39). A long follow up period will allow us to study the influence of a smoke free environment at home on the smoking initiation rates in teenage years. There is a dearth of longitudinal and experimental studies in this area. It would be a missed opportunity not to follow up these children in their teenage years and to attempt to address this key knowledge gap. In addition, interventions such as SFH can be seen as a long-term investment in public health, therefore, follow-up assessment is important to understand the sustainability of outcomes and to support on-going informed decision-making.

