At follow up 2 (11 months post intervention), follow up 3 (24 months post intervention), follow up 4 (36 months post intervention, follow up 5 (48 months post intervention), and follow up 6 (60 months post intervention) we will ask all children who remain in the trial to complete a children's survey (SO1, SO2, SO3, SO4). We will ask for a random sample of children who remain in the trial to provide a saliva sample at each follow up. This is to test the validity of the children's self reported smoking status in the survey (SO2) at different ages. The size of the random sample will be decided after baseline data collection, at which point we will be able to investigate how well children's self reported smoking status is validated by the results of the cotinine tests. Primary schools will oversee

the data collection for children who remain at their school. Secondary schools will oversee the data collection for participating children who have moved to their school.

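### The lifetime QALY and NHS-savings projection adjusts for later quitting but not for smoking that starts after the last follow-up, so it cannot tell delayed uptake from prevented uptake

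*Protocol*

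**What the plan says.** Under Economic Evaluation, Methods, the effect input to the long-term model is the "number of pupils who do not take up smoking in the intervention groups over and above the control scenario". Literature QALY values for smokers and non-smokers are attached to that excess "to project the potential QALY gains in the intervention group for those pupils who do not take up smoking". The step is conditional: the team will "estimate the gains that would be achieved should we demonstrate a significant reduction in smoking uptake". The same data feed the NHS side: "The data will also allow the modelling of potential health care cost savings amongst this population".

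The second half of that section describes the extrapolation. The trial data are combined with "existing quality of life values based on smoking status and age, which will be projected forward". One adjustment for later change in smoking status is named: "The modelling will adjust for natural quit rates in the population, so those smoking who would have given up anyway will be accounted for". Starting to smoke after the last follow-up is not mentioned. The section promises extensive sensitivity analyses over parameter values it does not list, and a threshold analysis of the long-term effectiveness needed to justify the cost.

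Two other places bear on this. Follow Up schedules the last assessment as "follow up 6 (60 months post intervention"). Justification for long follow-up reports that "38% of regular adult smokers started smoking before the age of 15 years".

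**The concern.** A projection of smoking status beyond the trial needs two movements: smokers who stop and non-smokers who start. The protocol names the first and not the second. Observation ends in mid-adolescence, when by the protocol's own figure most future regular smokers may not yet have begun. A pupil kept from smoking until the last assessment can still start a year later. If the model gives that pupil a lifetime non-smoker's QALYs and health care costs, a postponement has been valued as a permanent prevention.

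The section itself expects most of the benefit in the longer term, and the cost per QALY is read against a rule of at least 50% probability of being below £20,000. The projection therefore carries the trial's long-term value-for-money answer. Bootstrapping individual trial data does not help, because resampling cannot reveal a transition that the model lacks.

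**Working it through.** The protocol states no QALY gain, number of smokers averted or NHS saving, so there is no figure to reproduce. The check shows what the missing transition can do.

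**Inputs from the protocol**
- Age at recruitment: 9 to 11 years (Summary).
- Last follow-up: 60 months (Follow Up); the Summary says 63.
- Share of regular adult smokers starting before 15: 38% (Justification for long follow-up).
- Odds ratio for uptake, children with smoking parents: 1.56 (Sample Size Secondary outcomes). Used only in step 5.

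**Assumption not in the protocol**
- L, the proportion of pupils who would ever smoke regularly without the intervention: 20% to 40%.

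**Step 1: age when observation ends.** 9 + 5 = 14 to 11 + 5 = 16 years (14.25 to 16.25 at 63 months).

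**Step 2: starts at 15 or later.** 1 − 0.38 = 0.62. The cut is at 15, so part of this 62% falls inside follow-up for the older pupils.

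**Step 3: equal later initiation.** Control uptake by about age 15 is 0.38L. The risk of a later start among those not yet smoking is h = 0.62L / (1 − 0.38L). With uptake pc (control) and pi (intervention) at the last follow-up, and the same h in both arms, the lasting difference is

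[pc + (1 − pc)h] − [pi + (1 − pi)h] = (pc − pi)(1 − h).

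Crediting pc − pi in full overstates smokers averted by 1/(1 − h), which simplifies to (1 − 0.38L)/(1 − L).

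| L | h | Overstatement factor |
|---|---|---|
| 20% | 0.124/0.924 = 13.4% | 0.924/0.80 = 1.16 |
| 30% | 0.186/0.886 = 21.0% | 0.886/0.70 = 1.27 |
| 40% | 0.248/0.848 = 29.2% | 0.848/0.60 = 1.41 |

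To allow for older pupils being seen to about 16, suppose instead that 60% of starts have occurred by the last follow-up (assumed). At L = 20%, h = 0.08/0.88 = 9.1% and the factor is 0.88/0.80 = 1.10.

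**Step 4: pure delay.** If all averted early starters start later, the lasting difference in smokers is pc − pc = 0. Only the value of the smoke-free years gained remains.

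**Step 5: the effect persists.** Apply the odds ratio of 1.56 both to uptake by 15 and to later starts. At L = 20%:
- pc = 0.076. Odds 0.0823/1.56 = 0.0527, so pi = 0.050 and the credited difference is 0.0259.
- Later risk falls from 13.4% to 9.0% (odds 0.155/1.56 = 0.0994).
- Lifetime smokers in the intervention arm: 0.050 + 0.950 × 0.090 = 0.136. True difference: 0.200 − 0.136 = 0.064.
- Credited over true: 0.0259/0.0641 = 0.40. At L = 40% it is 0.0489/0.1091 = 0.45.

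Here the described model captures less than half of the lifetime reduction.

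**The case against.** The strongest reply is that the section outlines a model not yet built. Nothing in it says later initiation is zero. It promises wide sensitivity analyses, and the threshold analysis varies long-term effectiveness, which is where decay or catch-up would enter. A detailed plan is also promised before analysis.

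Part of this stands: the protocol is silent on later starts and does not rule them out. But it does fix the effect input and the one correction to later status. Naming exit without entry is a one-sided choice in the base case. Sensitivity analyses over unlisted parameters do not put the missing transition there. A threshold analysis says how much lasting effect is needed, not whether the measured effect lasts.

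Some stronger conclusions that a reader might draw are not supported:

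- **Every non-smoking pupil is credited as a prevented smoker.** The protocol counts only the excess over control. With L assumed at 25% and the odds ratio of 1.56, that is about 32 per 1,000 pupils, against about 937 per 1,000 who are simply not smoking.
- **The gains are certainly overstated.** Step 5 shows the opposite if the effect persists. Clustering in secondary schools and families expects later influences on smoking to act alike in both arms. That favours equal later initiation as a base case, but it concerns the secondary-school years and proves nothing about later ages.
- **62% of starts are missed.** The figure comes from a general survey of adult smokers and is cut at 15, while some pupils are seen to 16.
- **The gain is doubled.** That needs an assumed 50% later-start risk, for which the protocol gives no basis.

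Two limits on the arithmetic also stand. The factor counts smokers averted and gives no value to smoke-free years before a later start. And nothing shows that it would reverse the £20,000 conclusion: Cost of the intervention gives £36,000 for 50 schools, or £720 per school, but the protocol offers no QALY gain to set against it.

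**Conclusion.** The point holds as a gap in the described model: it moves pupils out of smoking after the trial but never into it, while observation stops at about 14 to 16 with much uptake still to come. It cannot separate delayed from prevented uptake. The direction of the error depends on what happens after follow-up:

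- overstatement of smokers averted by roughly 1.1 to 1.4 times under equal later initiation;
- loss of most of the gain under pure delay;
- understatement if the effect persists, with the credited difference at about 40% to 45% of the true one in the illustration.

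The sizes rest on L of 20% to 40%, which the protocol does not give, and on applying the 38% survey figure to this cohort. The gap itself rests only on the protocol's text. The same gap affects the NHS savings, which use the same uptake data.

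**What to change.** In Economic Evaluation, Methods, where the quit-rate adjustment is described, add a literature-based, age-specific rate of smoking initiation after the last follow-up, applied in both arms to pupils not yet smoking. Specify:

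- **Base case:** equal later initiation in both arms among those not yet smoking.
- **Scenario 1:** the relative effect seen in the trial persists into later initiation.
- **Scenario 2:** the arms converge fully, so that the intervention only delays uptake.

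Apply all three to the QALY gains and to the NHS cost savings, and carry them through to the acceptability curves.

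The cost is one extra literature-based transition and two scenarios in a model still to be built, with no change to data collection. The base-case gain will probably look less favourable.
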